# APPENDIX 1. SCHEDULE OF STUDY PROCEDURES

	6 0/7- 13 6/7 weeks GA	Randomization /Enrollment	Bi-weekly after enrollment	4 weeks after enrollment	monthly after enrollment	16-20 weeks GA	26-30 weeks GA	34 weeks GA	36 weeks GA until delivery	6 weeks Post-Partum	As needed
Screening											
• Initial eligibility	X										
• Ultrasound	X										
Consent	X										
Clinical Assessments											
• Physical exam		X									
• Medical history		X									
• Use of other medicines		X	X								
• Maternal Hb monitoring		X		X			X				
• BP Monitoring		X				X	X	X	X		
Medication Activities											
• Instructions for drug use		X									
• Medication compliance			X								
• Resupply					X						
Outcome Assessment											
• Preterm Birth										X	
• SGA										X	
• Preeclampsia/ Eclampsia			X							X	X
• Other maternal outcomes			X							X	X
• Other fetal outcomes										X	X
• Unanticipated medical care											X
• Serious Adverse Events											X

## APPENDIX 3. OUTCOME DEFINITIONS

---

### **PRIMARY OUTCOME:**

- ***Preterm Birth:*** delivery at or after 20 0/7 weeks and prior to 37 0/7 weeks.
  - **WHO definition:** babies born before 37 completed weeks of pregnancy.
  - **ACOG definition:** Birth occurs between 20 weeks and 37 weeks of pregnancy (<http://www.acog.org/~/media/For%20Patients/faq087.pdf>)

### **SECONDARY OUTCOMES:**

- ***Preeclampsia:*** characterized by hypertension and proteinuria occurring after the 20th week of pregnancy. Hypertension is a blood pressure of 140/90 mm Hg or above. In severe pre-eclampsia the diastolic blood pressure is usually 110 mm Hg or above and there may also be one or more of the following symptoms: severe headache, blurred vision, nausea and/or vomiting, abdominal pain and a diminished urinary output, i.e., oliguria. ***Early onset Preeclampsia*** develops before 34 weeks of gestation.
- ***Eclampsia:*** Very serious complication of pregnancy characterized by convulsions and coma. It may be preceded by signs of pre-eclampsia or the onset may be rapid and sudden. Eclamptic fits can occur in pregnancy, labour or soon after delivery.
- ***Small for gestational age:*** newborns with weights below the 10th percentile for gestational age.
- ***Perinatal mortality:*** The number of stillbirths and deaths in the first week of life per 1,000 live births, the perinatal period commences at 22 completed weeks (154 days) of gestation and ends seven completed days after birth.

### **MATERNAL OUTCOMES OF INTEREST**

- ***Vaginal bleeding:*** Bleeding during pregnancy (i.e., WHO generally defines as 'light' or 'heavy' bleeding based on clinical symptoms)
- ***Antepartum hemorrhage:*** Bleeding from the genital tract at any time after the 22nd week of pregnancy and before the birth of the baby. There are two main causes of antepartum haemorrhage, placenta praevia and abruption placentae.
- ***Postpartum hemorrhage:*** Blood loss of 1000 ml or more from the genital tract after delivery and up to six weeks post-delivery. Common causes include atony (poor muscle tone) of the uterus or trauma to the genital tract, e.g. tears of the vagina, cervix, or lower segment of the uterus.
- ***Maternal mortality:*** the death of a woman during pregnancy (i.e. conception to delivery) and the puerperium (i.e. up to 42 days after delivery).
- ***Change in maternal hemoglobin:*** Hemoglobin level <7.0 gm/dL or a 3.5 gm/dL decrease between measurements.

### **FETAL OUTCOMES OF INTEREST**

- ***Preterm birth <34 0/7 weeks of pregnancy:*** live birth before 34 0/7 weeks of pregnancy are completed.

- **Birth weight <2500g and Birth weight <1500g:** Birth weight is defined as the first weight of the fetus or newborn obtained after birth. For live births, birth weight should preferably be measured within the first hour of life before significant postnatal weight loss has occurred, recorded to the degree of accuracy to which it is measured (WHO). Birth weight <2500 g is defined as low birth weight, whereas birth weight <1500 g is defined as very low birth weight.
- **Fetal Loss:** Spontaneous loss  $\geq$  16 weeks GA plus perinatal mortality.
- **Late abortion:** Spontaneous fetal loss  $\geq$  16 weeks.
- **Spontaneous abortion:** Premature expulsion of a non-viable fetus from the uterus at  $<$  20 weeks gestation.
- **Stillbirth:** Birth of a baby that shows no signs of life at birth (no gasping, breathing, heart beat or movement). (WHO). It may be a macerated or fresh stillbirth. The signs of maceration are discoloration and peeling of the skin leaving areas of raw tissue. The skull is usually soft, as the brain has become soft. The umbilical cord is usually stained a dark red or black. The amniotic fluid is usually darkly stained. Maceration is the result of the infant being dead for at least 12 hours. Macerated stillborn infants are assumed to have died before the onset of labor. Fresh stillbirths show no sign of maceration and have usually died during labor or shortly before the onset of labor.
- **Medical termination of pregnancy:** an operation or other procedure to terminate pregnancy before the fetus is viable.

**NOTE:** (WHO) at the end of the definition means the definition is from the 2006 WHO guide titled: *Integrated Management of Pregnancy and Childbirth Pregnancy, Childbirth, Postpartum and Newborn Care: A guide for essential practice.*

## APPENDIX 4. STUDY TIMELINE

	YEAR 1				YEAR 2				YEAR 3			
	Q1	Q2	Q3	Q4	Q1	Q2	Q3	Q4	Q1	Q2	Q3	Q4
Preparatory Activities												
▪ Document Development (Protocol, forms, etc.)												
▪ Procurement of drug and other materials												
▪ Approvals (IRB, ERC, Drug Authorities, etc.)												
▪ Site Preparation												
▪ Training												
Recruitment												
Data Cleaning and Analysis												

## LIST OF ABBREVIATIONS

Acronym	Definition
DCC	Data Coordinating Center
DMC	Data Monitoring Committee
DRC	Democratic Republic of the Congo
EmONC	Emergency Obstetric and Neonatal Care
GA	Gestational Age
GEE	Generalized Estimating Equation
GN	Global Network
ITT	Intention to Treat
LMP	Last menstrual period
MDG	Millennium Development Goals
mITT	Modified intention to treat
MNH	Maternal and Neonatal Health
PP	Per protocol
RCT	Randomized Clinical Trial
SAP	Statistical Analysis Plan
UN	United Nations

## 1. BACKGROUND AND PROTOCOL HISTORY

### Background and Rationale

Preterm delivery, defined as delivery prior to 37 weeks 0/7 days gestation, remains the dominant cause of neonatal morbidity and mortality throughout the world, (March of Dimes, 2012, Matthews, 2004, Anderson, 2003) and directly leads to 28% of neonatal deaths within the first seven days of life. (Beck, 2010) Moreover, it is responsible of up to 50% of pediatric neurodevelopmental disorders. (Goldenberg, 1998) Infants born prematurely are likewise at increased risk for a variety of long-term medical complications such as respiratory, gastrointestinal, cardiovascular, and metabolic disorders. (McCormack, 2002, Saigal, 2008)

Compounding the issue, the risk of preterm birth is highest in developing countries where an estimated 12% of births are preterm compared to 5-7% in developed countries. (Valero De Bernabé, 2004) Of the near 13 million preterm births worldwide in 2005, 11 million were in Africa and Asia. (Blencowe, 2010) Given the tremendous medical, financial and emotional burden of preterm birth in the developing world and the limited resources to provide postnatal care, any interventions with the potential to reduce the risk of preterm birth deserve consideration. If one were to choose an intervention, it would be one that is widely available, inexpensive, and safe for the mother and fetus. Low dose aspirin may be just such an intervention.

We intend to study the effects of LDA in nulliparous women for several reasons. First, although it would be of interest to study the effect of LDA in women at high risk for preterm birth (e.g. prior preterm birth), such women may undergo interventions intended to decrease their risk of preterm birth. Thus, a study in patients with prior preterm birth would have numerous potential confounders. Conversely, multiparous women with prior term births would be at very low risk for preterm birth and also be a suboptimal population to study. Nulliparous women appear to be an ideal population since they will not undergo special interventions in an attempt to avoid preterm birth. Also, it appears that the risk of preterm birth in nulliparous women is higher than for the general obstetric population. In summary, available data suggest that LDA may be a safe, widely available and inexpensive intervention that may significantly reduce the risk of preterm birth. However, this possibility needs to be proven in a properly designed RCT with preterm birth as the primary outcome. Such a clinical trial in a racially, ethnically and geographically diverse population could best be accomplished through the established infrastructure of the Global Network for Women's and Children's Health Research (Global Network or GN).

### Protocol History

The protocol was initiated in March 2016 under Protocol version 1.1. Protocol amendment 1.2 was generated in December 2016.

This study completed randomization during the summer of 2018, with follow-up completed approximately 9 months after the last participant is randomized. No formal interim analyses were planned nor completed for this study and as such, the first formal assessment for efficacy is planned for after completion of primary follow-up.

## 2. PURPOSE OF THE ANALYSES

This statistical analysis plan (SAP) contains detailed information about statistical analyses to be performed to assess the primary and secondary hypotheses outlined in the protocol (i.e. to evaluate

whether women who are treated with LDA daily beginning between 6 0/7 weeks and 13 6/7 weeks GA through 36 0/7 weeks GA will have a reduced risk of preterm birth from all causes, and whether these women will have reduced risk of small for gestational age (SGA) deliveries, reduced risk of eclampsia and preeclampsia during pregnancy, and reduced risk of infants who experience perinatal mortality. The results of these analyses will be included in the study manuscript(s). Additional exploratory analyses may be performed to support further manuscript development. These analyses will not require an update to the SAP, but abbreviated analysis plans will be prepared prior to conducting those analyses.

### **3. STUDY OBJECTIVES AND OUTCOMES**

#### **3.1 Primary Hypothesis and Associated Outcomes**

Our primary hypothesis is that nulliparous women with no more than two previous first trimester pregnancy losses who are treated with LDA daily beginning between 6 0/7 weeks and 13 6/7 weeks GA through 36 0/7 weeks GA will reduce the risk of preterm birth from all causes.

The primary outcome of this study is preterm birth, which will be defined as delivery at or after 20 0/7 weeks and prior to 37 0/7 weeks. This will be determined based on actual date of delivery in comparison to the projected EDD, independent of whether or not the preterm delivery is indicated or spontaneous.

#### **3.2 Secondary Hypotheses and Associated Outcomes**

The study will also test three secondary hypotheses:

- Infants of women who take antenatal daily LDA initiated at 6 0/7 to 13 6/7 weeks GA will be at lower risk of being small for gestational age (SGA).
- Women who take antenatal daily LDA initiated at 6 0/7 to 13 6/7 weeks GA will have lower risk of: eclampsia and preeclampsia. Note that this hypothesis will be operationalized as evidence of hypertensive disorders of pregnancy as defined in more detail in Sections 9 and 12.
- Infants of women who take antenatal daily LDA initiated at 6 0/7 to 13 6/7 weeks GA will be at lower risk of perinatal mortality.

These secondary hypotheses will be tested using the following outcomes.

- Small for gestational age infants include newborns with weights below the 10th percentile for gestational age, as defined by Intergrowth Standards.
- Risk of Pregnancy Induced Hypertension (eclampsia and/or preeclampsia) defined as a binary outcome of any of new onset hypertension that occurs beyond 20 weeks gestational age, preeclampsia, or eclampsia happening between initiation of study dosing and participant completion of the study at 6 weeks after delivery. Eclampsia is a serious complication of pregnancy characterized by convulsions and coma. It may be preceded by signs of pre-eclampsia or the onset may be rapid and sudden and can occur in pregnancy, labor or soon after delivery. Preeclampsia is characterized by hypertension and proteinuria occurring after the 20th week of pregnancy. See Sections 9 and 12 for more detail.

- Perinatal mortality is a binary outcome that includes any stillbirth occurring after 20 weeks pregnancy and any early neonatal death that occurs within 7 days after delivery.

### **3.3 Other Outcomes of Interest in this Study**

Study analyses will examine a number of additional maternal and fetal or neonatal outcomes to assess whether use of LDA daily beginning between 6 0/7 weeks and 13 6/7 weeks has an effect on those outcomes. Specific maternal and fetal/neonatal outcomes include:

**Maternal outcomes:**

- Vaginal bleeding
- Antepartum hemorrhage
- Postpartum hemorrhage
- Maternal mortality
- Late abortion
- Preterm, preeclampsia

**Fetal/Neonatal outcomes:**

- Preterm birth <34 0/7 weeks of pregnancy
- Birth weight <2500g and <1500g
- Fetal loss
- Spontaneous abortion
- Stillbirth
- Medical termination of pregnancy

Detailed definitions of these outcomes are included in Section 9. Change in maternal hemoglobin is an other/exploratory outcome collected for this study. Analyses of these data will be performed for a secondary manuscript and are not covered under this analysis plan.

## **4. STUDY METHODS**

[figure not shown]
### **4.1 Overall Study Design**

The ASPIRIN trial was conducted as a randomized, placebo-controlled, double-blinded multicenter clinical trial to assess the efficacy of LDA in the reduction of preterm birth. Women were randomized equally to receive either daily LDA (81 mg) or an identical appearing placebo beginning between 6 0/7 weeks and 13 6/7 weeks GA and continuing until 36 0/7 weeks GA or delivery.

The study intervention is 81 mg of aspirin administered daily beginning between 6 0/7 weeks and 13 6/7 weeks through 36 0/7 weeks or delivery. Following randomization, each woman was to be provided with a supply of either LDA or an identical appearing placebo. The drug or placebo were enteric coated pills, provided in identical, child-resistant packaging, with written instructions for use. To ensure that literacy levels did not affect proper use, the study staff was to provide verbal instructions at randomization and reinforce these guidelines at subsequent follow-up visits. Each woman was to also receive a back-up supply of medication or placebo, which will be maintained throughout the duration of the study. The purpose of the backup is to bridge circumstances wherein the woman misses or is late to a planned follow-up visit or the primary supply of study drug/placebo is misplaced or destroyed. Medication compliance was to be monitored, and the drug/placebo supply was to be replenished during routine study visits.

A study schematic is shown below

## Study Schematic

## 4.2 Study Population

Studying the effect of LDA in women at very high risk for preterm birth (e.g., prior preterm birth) would have numerous confounders, as these women are likely to undergo interventions intended to

decrease their risk. Conversely, multiparous women with prior term births would be at very low risk for preterm birth, making them a suboptimal study population. Nulliparous women appear to be the ideal population to study the effects of LDA since they will not undergo special interventions to avoid preterm birth. Multiple studies have shown that the risk of preterm birth in nulliparous women is higher than for the general obstetric population.

### **Inclusion criteria**

- Nulliparous women between 18 – 40 years of age. Minors who are  $\geq$  14 years of age may be enrolled if permitted by the country's ethical guidelines.
- No more than two previous first trimester pregnancy losses
- No medical contraindications to aspirin;
- Single live intrauterine pregnancy (IUP) between 6 0/7 and 13 6/7 weeks GA corroborated by an early dating ultrasound and with a fetal heart rate detected.

### **Exclusion criteria**

- Women prescribed daily aspirin for more than 7 days;
- Multiple gestations;
- Fetal anomaly by ultrasound (Note most fetal anomalies are not detectable by ultrasounds done at this early gestation. Subsequent discovery of a fetal anomaly is not viewed as an exclusion.);
- Hemoglobin  $< 7.0$  g/dl at screening;
- Systolic blood pressure  $\geq 140$  and diastolic  $\geq 90$  at screening;
- Any other medical conditions that may be considered a contraindication per the judgment of the site investigator (e.g., Lupus, Type 1 Diabetes, or any other known significant disease)

### **4.3 Study Arm Assignment and Randomization**

Randomization of subjects was carried out to obtain a 1:1 allocation ratio between the treatment and placebo arms. Randomization was stratified by site. A computer algorithm generated by the data coordinating center (DCC) was created the random assignment to one of the treatment arms based on randomly permuted block design with randomly varied block sizes. The block sizes were known only by the DCC personnel. A total of 11,920 nulliparous women were to be enrolled (5960 per group) across seven sites in sub-Saharan Africa, South Asia, and Latin America. For balance, each site was to enroll no more than 25% of the total sample.

To study the possible effect of LDA on anemia, an ancillary study was to enroll at least 500 women to obtain hemoglobin measure at 4 weeks after initiation of therapy, with each site contributing at least 75 women to that sample. Some sites ultimately collected hemoglobin 4-weeks post randomization for all participants. In addition, hemoglobin measures were to be obtained from all women at 26 to 30 weeks gestational age. The analyses of this ancillary study will be described in a separate analysis plan document and will not be included as part of the primary study publication.

### **4.4 Masking and Data Lock**

Both the formulation of the medication and placebo were procured from two manufacturers, with one manufacturer supplying materials for Pakistan participants and the other manufacturer supplying

materials for the participants at the other sites. The packaging was standardized across sites and labeled as ASA 81 mg/placebo, with the expiration date and a unique identifier. A certificate of authenticity was to likewise be provided. Manufacturing details are maintained in the study file.

Throughout the study, research staff and local health providers were masked to treatment status unless there was a serious adverse event potentially related to the treatment modality that requires unmasking for safety reasons. There was one pharmacist at each site who was to remain unmasked to monitor randomization, drug supply, and safety as needed.

**Data Lock:** Data will be locked at the site level with final analysis data sets generated and locked once data from all sites have been received and all queries processed. For each site, data collection for the protocol will stop approximately 9 months after the last pregnant woman was randomized into the study at that site. Site will transmit all data forms to the site within three months of this date, and data will be locked three to six months post last follow-up visit. Note that other than for the cases on individual unmasking described above, which are anticipated to be minimal, the study will not be unmasked until after data lock.

## 5. ANALYSIS POPULATIONS

### Safety (SAF) Population

The safety population will comprise all randomized participants who received any study treatment grouped by actual treatment received, irrespective of amount or duration of treatment received. Unless specified otherwise, data for this population will be analyzed as available (i.e. irrespective of protocol deviation occurrence, subsequent study participation termination, or study drug withdrawal).

### Modified Intention to Treat (mITT) Population

**The primary analysis population will be the modified intention to treat population**, which includes all eligible, randomized participants who provide any post-baseline outcome data and who deliver at 20 weeks gestational age or greater. All participants will be assigned to the arm to which they were randomized irrespective of treatment received. Unless specified otherwise, data for this population will be analyzed as available (i.e. irrespective of protocol deviation occurrence, subsequent study participation termination, or study drug withdrawal). This population will also be used for many of the secondary analyses. Note that this population represents a change from the protocol, which indicates that the ITT population will be used for the primary analyses. This change was made prior to any unmasking.

### Intention to Treat (ITT) Population

The intention to treat population will include all eligible, randomized participants. All participants will be assigned to the arm to which they were randomized irrespective of treatment received. Unless specified otherwise, all participants will be included in analyses using this population (with data imputed as needed and irrespective of protocol deviation occurrence, subsequent study participation termination, or study drug withdrawal). This population will be used to conduct sensitivity analyses for the primary outcome.

### Per Protocol (PP) Population

This population will be used to conduct sensitivity analyses for the primary outcome. This population will exclude all or part of the data obtained from any eligible, randomized participants who deliver at 20 weeks gestational age or greater that did not receive at least 90% of the full amount of intended randomized study therapy or are considered to have substantially deviated from the protocol in a manner that may impact study outcome or treatment receipt. The population will also exclude individuals who were randomized after 10 weeks, 6 days gestational age. Participants will be grouped by actual treatment received. Treatment receipt reasons and substantial deviations that will lead to exclusion include:

- Documented receipt of aspirin while on study outside of assigned study drug as identified by a reported protocol deviation
- Not receiving treatment after randomization: All data from these participants will be excluded.
- Receipt of less than 90% of planned total doses after randomization where the number of planned doses will be calculated as those expected between randomization and the earliest of end of pregnancy and 36 0/7 weeks GA irrespective of if study drug administration was prematurely discontinued for any reason prior to that point: All data from these participants will be excluded.

Receiving more than the planned total doses of study drug will generally NOT be an exclusion criterion for the PP population. Additional exclusion reasons may be identified after completion of participant enrollment. Any participant deviations that will exclude participants or their data from the PP analyses will be identified by the study team, prior to review of efficacy and safety data, as a part of a masked data review to reduce the opportunity for introducing of bias and will be documented in an addendum to this analysis plan.

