## **9. EFFICACY ANALYSES**

### **9.1 Overview of Efficacy Analysis Methods**

The primary efficacy analyses will be performed using the mITT population. All other efficacy analyses will be performed either using the mITT, ITT or per-protocol population as detailed below. The data will be summarized by treatment arm, overall and by country. All model-based analyses and test-statistics examining the treatment effect will adjust for GN site as a randomization variable. Additional details are presented in the sections below.

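### The per-protocol set drops every woman randomised from 11w0d although entry runs to 13w6d, so it mixes timing of start with adherence and a PP–mITT difference could not be attributed

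*Combined protocol and SAP*

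**What the plan says.** SAP Section 4.2 admits women with a "Single live intrauterine pregnancy (IUP) between 6 0/7 and 13 6/7 weeks GA". SAP Section 3.1 states the primary hypothesis for women "treated with LDA daily beginning between 6 0/7 weeks and 13 6/7 weeks GA through 36 0/7 weeks GA". Both reach 13w6d.

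SAP Section 5 removes from the PP set women who "did not receive at least 90% of the full amount of intended randomized study therapy" or who substantially deviated from the protocol. It then adds: "The population will also exclude individuals who were randomized after 10 weeks, 6 days gestational age". The dose rule is spelled out as "Receipt of less than 90% of planned total doses after randomization", with planned doses counted from randomisation to the earlier of the end of pregnancy and 36w0d.

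The role of the set is stated once: "This population will be used to conduct sensitivity analyses for the primary outcome". The main analysis is elsewhere: "The primary efficacy analyses will be performed using the mITT population", and the mITT definition has no gestational-age cut inside the entry window.

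SAP Section 8.2 splits gestational age at first dose at 10 weeks, not at 10w6d. The Table 2 shell bands gestational age at enrolment with a break after 10w6d. Section 12, which lists changes from the protocol, does not mention the cut, and the protocol's analysis section (3.1) defines no PP set.

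**The concern.** A PP analysis is normally read as showing what happens among women who followed the protocol. Here, following the protocol is not enough: a woman randomised between 11w0d and 13w6d is excluded however well she adhered. Nor is the cut needed to treat later starters fairly on dose, because the 90% rule already counts only the doses planned after each woman's own randomisation.

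The set therefore changes two things at once relative to mITT: it requires adherence, and it restricts the population to early starters. If the PP estimate is stronger than the mITT estimate, one reader will credit adherence and another early initiation. If it is weaker or its interval is wide, the loss of later entrants is a third possible explanation. What is at stake is the interpretability and precision of a sensitivity analysis of the primary outcome.

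**Working it through.** **1. Does any other planned analysis separate timing from adherence?**

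- SAP 7.4, 9.4 and 9.5: the only planned look at heterogeneity of effect is by site.
- SAP 8.2: gestational age at first dose, adherence and exposure are summarised descriptively by arm. No treatment effect is estimated by timing.
- SAP 7.3 and 9.4: the sensitivity analyses address early losses and missing data (ITT with early losses counted as preterm, inverse probability weighting, multiple imputation).
- No PP set without the cut is defined, and no mITT estimate by gestational age at randomisation.

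So the two components are not separated anywhere in the plan.

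**2. Reproduce the plan's sample size.** Inputs from SAP 6.1 and 7.5: 8.0% vs 6.4%, two-sided 5%, 90% power, 1:1.

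n per arm = [1.960·√(2p̄q̄) + 1.282·√(p₁q₁ + p₂q₂)]² / (p₁ − p₂)², with p̄ = 0.072 and q = 1 − p.

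√(2 × 0.072 × 0.928) = 0.3656 and √(0.0736 + 0.0599) = 0.3654, so n = (0.7165 + 0.4683)² / 0.016² ≈ 5,483. This matches the plan. Dividing by 0.92 gives 5,960, which also matches.

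**3. Share removed by the cut.** The documents do not give the distribution of gestational age at entry, so every line below is an assumption.

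The window 6w0d–13w6d has 56 days, of which 11w0d–13w6d is 21.

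- Uniform entry: 21/56 = 37.5%.
- Density falling linearly to zero: (21/56)² = 14.1%.
- Density rising linearly from zero: 1 − (35/56)² = 60.9%.
- Normal truncated to the window, SD 1.5 to 2 weeks: mean 9 weeks, 9–16%; mean 10 weeks, 25–30%; mean 10.5 weeks, 36–38%; mean 11 weeks, 47–49%.

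These shapes span about 9% to 61%. More extreme means go further (8 weeks: 2.5–8%; 12 weeks: 63–72%).

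**4. Power in what remains.**

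Power = Φ{[(p₁ − p₂)√n − 1.960·√(2p̄q̄)] / √(p₁q₁ + p₂q₂)}.

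For uniform entry, n = 5,483 × 0.625 = 3,427, and for 8.0% vs 6.4%: Φ[(0.016 × 58.54 − 0.7165)/0.3654] = Φ(0.60) = 73%.

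| Share removed | n per arm, all adherent | Power, 8.0% vs 6.4% | n per arm, 80% meet dose rule (assumed) | Power, 8.0% vs 6.4% |
|---|---|---|---|---|
| 0% (no cut) | 5,483 | 90% | 4,386 | 83% |
| 9.3% | 4,973 | 87% | 3,978 | 79% |
| 37.5% (uniform) | 3,427 | 73% | 2,742 | 63% |
| 60.9% | 2,142 | 53% | 1,713 | 44% |

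For 8.0% vs 6.0%, uniform entry gives 90% power with 3,427 per arm and 83% with 2,742. This agrees with protocol Table 2, which needs 3,419 per arm for 90% power at a 25% reduction.

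The table assumes that adherence does not vary with gestational age at entry.

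**5. Power of an interaction test by entry age.** Take the uniform split (3,427 early and 5,483 − 3,427 = 2,056 late per arm), control risk 8%, and assumed relative risks of 0.75 early and 0.90 late. The standard errors of the log relative risks are 0.089 and 0.109, so z = |ln(0.75/0.90)| / √(0.089² + 0.109²) = 0.182/0.141 = 1.30 and power is about 25%. With 0.72 and 0.93 it is about 44%.

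**The case against.** The strongest defence is that the SAP gives this set only a sensitivity role and never says that it isolates adherence. Early start plus at least 90% of doses can be read as a best-exposure analysis, in keeping with protocol Section 1.3.1, which argues that aspirin may work best if begun in the first trimester. On that reading the dispute is largely about the label. This stands in part: the set is worth keeping. But the protocol's rationale concerns the first trimester and starts before 16 weeks. It does not point to 10w6d, and the SAP itself uses 10 weeks in Section 8.2.

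A reader might infer that the set loses over a third of compliant women. The documents do not support that as a fact; it needs roughly uniform or later entry. Likewise, 73% power belongs to one effect size, and if early starters benefit more, as the protocol argues, power is higher. No document claims that the PP analysis was powered.

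A reader might also infer bias in the main result. That does not follow. The formal test uses mITT, which has no such cut, and gestational age at randomisation is a baseline variable, so this cut alone does not unbalance the arms.

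It would also be too strong to call the ambiguity irreparable. The entry-age bands in the Table 2 shell and the adherence summaries use data already collected. They do not supply an effect estimate by entry age, however, so the gap remains in the plan as written.

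**Conclusion.** The point holds as one of definition and interpretation. The PP set excludes women who complied fully with the protocol, the documents give no reason, and no planned analysis would show whether timing or adherence lay behind a PP–mITT difference. This requires only that some compliant women entered at 11w0d or later.

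The cost in precision is uncertain. Under the assumed entry shapes, 9% to 61% of women are lost and power for 8.0% vs 6.4% runs from about 87% to 53% before any adherence loss. Uniform entry gives 37.5% and 73%, or 90% power if the effect is 8.0% vs 6.0%. The primary conclusion of the trial does not depend on it. It should be corrected, but it does not threaten the main inference.

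**What to change.** - Define PP by adherence and substantial deviations over the full 6w0d–13w6d window, deleting the gestational-age sentence.
- Keep the early-start adherent set as a separate analysis under its own name, with the reason for its cut-point stated.
- Prespecify a descriptive mITT estimate of the treatment effect, with confidence intervals, for women randomised up to 10w6d and from 11w0d. Label any interaction test exploratory and low-powered (about 25% to 44% in the two scenarios worked above).
- Reconcile the 10w6d cut with the 10-week split in SAP 8.2, and record the change in Section 12. The addendum already planned for the masked data review (SAP 5 and 7.6) is a natural place, provided it is completed before unmasking.

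The cost is SAP wording and one more exploratory analysis to report, on data already collected.
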